8. SAFETY REPORTING

The Investigator is to report all directly observed AEs, all AEs spontaneously reported, or pregnancies by the study subject (or subject's partner). In addition, each study subject will be questioned about AEs and pregnancies (if applicable) at each clinic visit. As the Sponsor, ViaCyte is responsible for collecting and evaluating reported safety data in accordance with applicable regulatory requirements and as outlined in Sponsor SOPs and Safety Management Plan.

8.1. Adverse Events

An adverse event (AE) is any untoward medical occurrence in a clinical investigation subject administered a product or medical device. Adverse events need not necessarily have a causal relationship with the treatment or usage.

Examples of AEs include, but are not limited to:

- Abnormal test findings;
- Clinically significant symptoms and signs (changes from baseline status);
- Clinically significant changes in physical examination findings;
- Hypersensitivity;
- Sensitization to the line;
- Progression/worsening of underlying disease (includes worsening diabetes)

All observed or volunteered AEs regardless of suspected causal relationship to the investigational product will be reported as described in the following sections. Non-clinically significant physical exam observations will not be reported as an AE.

For all AEs, the Investigator must pursue and obtain information adequate both to determine the outcome of the AE and to assess whether it meets the criteria for classification as a serious adverse event (SAE) requiring immediate notification to the Sponsor and the Ethics Committee. For all AEs, sufficient information should be obtained by the Investigator to determine the causality of the AE. The Investigator is required to assess causality. Follow-up by the Investigator may be required until the event or its sequelae resolve or stabilize at a level acceptable to the Investigator, and the Sponsor concurs with that assessment.

As part of ongoing safety reviews conducted by the Sponsor, any non-serious AE that is determined by the Sponsor to be serious will be reported by the Sponsor as a SAE. To assist in the determination of case seriousness, further information may be requested from the Investigator to provide clarity and understanding of the event in the context of the clinical trial.

As required on the AE CRFs, the Investigator will use the National Cancer Institute Common Terminology Criteria for Adverse Event (NCI-CTCAE) guidelines to describe the maximum intensity of the AE. For purposes of consistency, these intensity grades are defined as follows:

| MILD | Asymptomatic, or mild symptoms, clinical or diagnostic observations noted; intervention not indicated |
|------------------|---|
| MODERATE | Local or noninvasive intervention indicated |
| SEVERE | Medically significant but not immediately life threatening, hospitalization or prolonged hospitalization. |
| LIFE-THREATENING | Life-threatening consequences, urgent intervention indicated |
| DEATH | Death related to AE |

Note the distinction between the severity and the seriousness of an AE. A severe event is not necessarily an SAE. For example, a headache may be severe (medically significant) but would not be classified as serious unless it met one of the criteria for SAEs (See Section 8.2).

Likewise, AEs may receive a temporal classification based on the start date of the event relative to when the investigational product was first administered. A treatment emergent AE (TEAE) is defined as an AE that starts on or after the date of implant surgery.

In addition, if the Investigator determines an SAE is associated with study procedures, the Investigator must record this causal relationship in the subject's source documents and CRF, as appropriate, and report such an assessment in accordance with the SAE reporting requirements, if applicable.

It should be noted that the form for collection of SAE information will not be the same as the AE CRF. Where the same data are collected, the forms must be completed in a consistent manner. AEs should be reported using concise medical terminology.

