8.1.5. Period of Observation and Reporting

All AEs for Cohort 1 with a start date occurring between Visit 3 (Day 1) and through the last subject visit must be recorded on the CRF. All AEs for Cohort 2 with a start date occurring between Visit 2 (Week -4) and through the last subject visit must be recorded on the CRF. During the study, sites should query subjects on the status of any ongoing AEs at subsequent clinic visits. Depending on the reported event, the Investigator may need to follow-up on the status of AEs with the study subject between visits (e.g., phone, text, or email). At the conclusion of the trial, any ongoing AEs will be followed until at least 28 days after the final explantation procedure to determine the final reported outcome of the event.

For SAEs, and pregnancy reports, the active reporting period to the Sponsor begins from the time the subject provides informed consent through and including 28 days after the final explantation of all of the investigational product units.

SAEs and pregnancies occurring after the period of observation has ended should be reported to the Sponsor if the Investigator becomes aware of an event. At a minimum, all SAEs the Investigator assesses as possibly related to the investigational product are to be reported to the Sponsor.

The reporting period for AEs and SAEs may overlap with the timing of the subject's participation in the separate follow-up study. Further details on how to report ongoing AEs spanning the period between this protocol and the separate follow-up study will be outlined in the separate follow-up protocol.

All AE reporting, including SAEs and suspected unexpected serious adverse reactions (SUSARs), will be carried out in accordance with applicable regulations.

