8.6. Study Stopping Rules

If any of the following safety events are noted to occur in the study, an ad-hoc meeting of the DSMB will be requested. The DSMB will review the data and can recommend stopping the study for any of the following:

- 1. Two or more subjects have pronounced immune responses to VC-01.
- 2. Two or more subjects experiencing an NCI-CTCAE Grade 3 (severe) treatment emergent adverse event (TEAE) in the same Medical Dictionary for Regulatory Activities (MedDRA) system organ class (SOC) and preferred term (PT) considered to be possibly or probably related to the investigational product. TEAE is defined as an AE that starts on or after the date of implant surgery.
- 3. After a minimum of eight weeks post-implantation, there are two or more subjects who each experience two or more Severe Hypoglycemic Events (SHE) over a 6-month period unrelated to anything other than VC-01. This assumes the SHE occurred despite reasonable adjustments in the exogenous insulin requirements and appropriate dietary adjustments.
- 4. Two or more subjects develop SAEs deemed related to the implantation of VC-01 itself; examples of such events are noted below:
 - a. Development of an off-target cell growth (i.e., teratoma) within the unit which is noted on ultrasound and confirmed by pathologist.
 - b. A related, severe, persistent, inflammatory response that does not resolve (e.g., severe site reactions, urticaria, erythematous rash, anaphylaxis, acute respiratory insufficiency, swelling).
- 5. Two or more subjects have an unexplained graft malfunction requiring explant.

In addition to these events, the DSMB can consider recommending a temporary delay or hold on enrollment in the trial for events considered by the Investigator to be related to VC-01. The DSMB can also recommend treatment continue for a shorter duration (i.e., less than the planned 6 months (Cohort 1) or 12 months (Cohort 2)) or with a fewer number of implanted units. The DSMB can also recommend the Sponsor close the study at any time in response to any legitimate safety

concerns. The Sponsor will communicate DSMB recommendations to each site in a timely fashion. Each site's Ethics Committee will make the ultimate decision to delay enrollment, modify treatment duration, or stop the study based on DSMB recommendations.

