## Blood glucose value only:

- If a first timepoint is missing, the value will be imputed as the average of the first available timepoint and zero (the value '0'). If multiple timepoints were missed at the start of an MMTT, the timepoints will be imputed using this same formula, in reverse order (starting with the latest missing timepoint and repeating for each subsequent missing value until the 0 minute timepoint has been imputed).

For AEs, it is expected that complete start and end dates will be provided for all reported AEs. Therefore, no imputation for missing or partial dates is needed for AEs. No additional imputations will be performed for any other missing data in this study.

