## 7.3.7.2 Cohort 2 Secondary Safety Analyses

Unless otherwise specified, the SAS will be used for the safety summarizations for the Cohort 2 subjects. Adverse events and SAEs will be summarized by system organ class (SOC), by severity, and by relationship. This will be done by treatment group and overall. As with the Cohort 1 subjects, the summarization of AEs for Cohort 2 will focus on only those events that are TEAEs, but the AE listings will include all reported AEs regardless of when they started.

Other safety data, such as vital signs, clinical laboratory data, and hypoglycemic events will be summarized by study visit and treatment group, for the Cohort 2 subjects. Change from baseline in safety data will also be summarized in a similar manner. Physical examination data will be listed by subject.

The number of Cohort 2 subjects experiencing off-target growth as evidenced by implanted VC-01 units via lumen ultrasound (lumen thickness > 1 mm) measurements, or by histological examination of explants will be summarized by treatment group.

For immune response as measured by serum immunoglobulin and hematological assays, any Cohort 2 subject who appears to be having an immune response will have all relevant data described in a clinical narrative. In addition, data of interest from the assays may be summarized by treatment group and overall. For the incidence of immune sensitization, a listing will be provided for all subjects with a suspected event (the presence of donor anti-HLA antibodies absent prior to implant), with a column in the listing that indicates whether it is a confirmed immune sensitization (either confirmatory histological observations from at least one explanted unit and/or the presence of clinical symptoms; will have a corresponding 'sensitization' AE).

Implantation site assessments will be summarized at each time-point post-implantation and each visit thereafter. For each site assessment symptom, the number of Cohort 2 subjects with the symptom at that time-point will be summarized by treatment group and overall.

Finally, the number of Cohort 2 subjects undergoing a premature VC-01 unit explant will be provided in a listing (separate from the overall explant listing), which includes the reason for explantation (i.e., safety issue, malfunction, damaged, planned explant, etc.).

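### A TEAE is defined by start date alone, so a Cohort 2 event that begins in screening and worsens after implant can fall outside the TEAE summaries and stopping rule 2

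*Protocol*

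**What the plan says.** Protocol 8.1 defines the term: "A treatment emergent AE (TEAE) is defined as an AE that starts on or after the date of implant surgery". Section 8.6 repeats it inside stopping rule 2: "TEAE is defined as an AE that starts on or after the date of implant surgery". The SAP uses TEAE and treatment-emergent SAE throughout 7.3.7.1 and 7.3.7.2 but does not define either term afresh.

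Severity is one value per event. Section 8.1 has the investigator use CTCAE "guidelines to describe the maximum intensity of the AE".

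The recording windows in Protocol 8.1.5 differ by cohort. For Cohort 2 the window opens before implant: "All AEs for Cohort 2 with a start date occurring between Visit 2 (Week -4"). For Cohort 1 it opens on the day of implant: "All AEs for Cohort 1 with a start date occurring between Visit 3 (Day 1) and through the last subject visit must be recorded". SAEs in both cohorts are reportable from consent.

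On presentation, SAP 7.3.7.2 says "the summarization of AEs for Cohort 2 will focus on only those events that are TEAEs". SAP 7.3.7.1 says the same for Cohort 1. In both cohorts the listings carry every reported event, whatever its start date.

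**The concern.** A treatment-emergent definition should capture what happens to the subject after treatment, including aggravation of something already present. This one captures only new onsets. That does no harm if nothing is recorded before treatment, or if each worsening gets its own dated record. In Cohort 2 the first condition fails and the second is not required.

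At stake are the Cohort 2 incidence tables, all built on TEAEs, and stopping rule 2, which counts only TEAEs. An event that surgery or product made worse, and that the investigator judged related, could be absent from both. Protocol 8.1.1 asks whether product or surgery caused the event or contributed to it, so a pre-existing event can properly be judged related.

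**Working it through.** The plan states no figure on this point, so the check traces one clinical course through the rules: onset in screening at a mild grade, becoming severe or serious after implant.

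**Cohort 2**

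1. Recording. The event starts between Visit 2 and implant. Protocol 6.2 requires at least two weeks between Visit 2 and Visit 3, and Visit 2 is nominally at Week -4, so the window is real for every subject. The event goes on the CRF with a pre-implant start date (8.1.5).
2. Grading. The record holds the maximum intensity (8.1). If the site keeps one record, the severe grade reached after implant sits beside the pre-implant start date. Neither document says to open a new record when the grade rises or the event becomes serious.
3. Classification. The start date precedes implant, so the record is not a TEAE under 8.1 or 8.6.
4. Summaries. The AE tables are restricted to TEAEs (SAP 7.3.7.1, 7.3.7.2), so the record appears in none of them, including those by grade, by relationship and for serious events.
5. Stopping rule 2. It counts Grade 3 related TEAEs, so the record does not contribute.
6. What remains. The record is in the AE listing. If serious, it is reported as an SAE. Stopping rule 4 is written in terms of related SAEs, not TEAEs, so it is unaffected.

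**Cohort 1, same course**

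- Literal reading: the start date precedes Day 1, so 8.1.5 does not require the event on the AE CRF (unless it is an SAE), and it fails the same TEAE definition. It is not counted.
- Alternative reading: the condition is treated as history, and its worsening is entered as a new AE dated on or after Day 1. It is counted. This reading rests on the statements that clinically significant changes from the screening examination and ECG are AEs (7.1.1, 7.1.3) and that worsening of underlying disease is an AE (8.1). Those statements apply equally to Cohort 2.

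The documents do not choose between these readings. There is also a loose end: the Cohort 1 schedule and Protocol 6.2 have AEs assessed at Visit 2, while 8.1.5 begins Cohort 1 recording at Visit 3.

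**Size**

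The only figure available is the planned maximum of 40 subjects in Cohort 2. One omitted subject changes an incidence by 1/40 = 2.5 percentage points. The number of omitted subjects would need a rate of events ongoing at implant and a rate of worsening. The documents give neither.

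**The case against.** The strongest reply is that the omission is conditional. It occurs only if the site keeps a single record, which no text requires; grading by maximum intensity does not forbid a new record, and 7.1.1, 7.1.3 and 8.1 point towards one for some kinds of worsening. That is correct. It is why the point is worded as a gap and not as a certain loss. A site that follows the text either way is compliant, so the tables would depend on local habit.

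The consequences are also limited. Listings in a trial of at most 40 Cohort 2 subjects can be read line by line. SAEs are reported from consent, and adverse events of special interest (8.1.4) are not restricted to TEAEs. Several of the commonest events in Protocol 1.4.2, such as procedural pain and incision site pain, cannot start before surgery. Stopping rule 2 needs two subjects with Grade 3 related events in the same system organ class and preferred term, so an arbitrary worsened event will rarely bear on it, and the DSMB may act on any genuine safety concern. All of this stands and keeps the point modest. It does not repair the summaries, which do not draw on the listings.

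Three stronger readings are tempting and are not supported:

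- *That the same course is counted in Cohort 1, so the safety comparison favours the higher-dose cohort.* No text makes Cohort 1 worsening a new AE, and the passages that might do so cover both cohorts. The documents show only that the recording windows differ and that neither cohort has a worsening rule, so handling may differ. No hypothesis test is planned (Protocol 10.1).
- *That one to four events would be lost.* Assuming 0.25 to 0.5 ongoing events per subject and 10% to 20% worsening gives 40 x 0.25 x 0.10 = 1 to 40 x 0.5 x 0.20 = 4, but neither rate has any basis in the documents, so the range only restates the assumptions.
- *That the date rule compounds the error.* SAP 7.2.4 says "Therefore, no imputation for missing or partial dates is needed for AEs" because complete dates are expected. A fallback would be prudent, but no resulting error is shown.

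**Conclusion.** The point holds in a limited form. The start-date-only definition, combined with pre-implant AE recording in Cohort 2, maximum-intensity grading and no new-record instruction, allows an event aggravated after implant to be left out of the TEAE and treatment-emergent SAE summaries and of stopping rule 2. This rests on one assumption: that the site keeps the event in a single record. The effect is probably small, and its size cannot be derived from the documents. No bias between cohorts is established. It is worth correcting because the rule as written can only undercount post-implant worsening, and correcting it is cheap.

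**What to change.** In Protocol 8.1 and the SAP, define a TEAE as an adverse event that starts, or increases in grade or becomes serious, on or after the day of implant surgery. Reconcile the definition restated in 8.6 with this wording; the stopping thresholds are not at issue and stay as they are.

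Pair the definition with one recording mechanism for both cohorts. For example, the site enters a new AE record dated at the worsening and linked to the original, and only the new record is counted as treatment-emergent. The dated record is needed because, as the documents describe it, the AE form carries a maximum grade but no date at which the grade changed. Counting only the new record matters because SAP 7.3.7.1 totals every TEAE episode, and counting both records would double the event. The same instruction should say how Cohort 1 events with onset before Day 1 are handled and settle the Visit 2 versus Visit 3 starting point.

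The cost is a wording change in two documents, one CRF completion instruction and a slightly higher TEAE count.

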8.1.1. Causality Assessment of Adverse Events

The Investigator's assessment of causality must be provided for all AEs (serious and non-serious). In relation to implantation with VC-01, there are two (2) main components to assessing causality. The Investigator's causality assessment must include a determination of whether there exists a reasonable possibility that:

- The investigational product (VC-01) itself caused or contributed to the AE.
- The surgical procedure (implantation or explanation) caused or contributed to the AE.

In evaluating the causal relationship of an AE to VC-01 and the surgical procedures, it is possible for the Investigator to determine causality as being associated to one or more of these factors. Conversely, the Investigator can determine that none of these relate to the AE.

If the Investigator's final determination of causality is unknown, and the Investigator does not know if the investigational product, surgical procedure, or immunosuppression drugs caused the event, then the event will be classified as "related to investigational product" for reporting purposes. If the Investigator's causality assessment is "unknown but not related to investigational product", this should be clearly documented on the subject's source records.

Relationship of an AE to VC-01 and the surgical procedures will be assessed as follows:

Not Related: A clinical event including laboratory test abnormalities without a temporal relationship to the investigational product exposure or the surgical procedures which makes a causal relationship improbable, and/or in which other drugs, chemicals, or underlying disease provides plausible explanations.

Unlikely Related: A clinical event including laboratory test abnormalities without any temporal relationship to the investigational product exposure or the surgical procedures which makes a causal relationship doubtful or unlikely and/or in which other drugs, chemicals, or underlying disease provides plausible explanations.

Possibly Related: A clinical event, including laboratory test abnormality, with a reasonable time sequence to exposure of the investigational product or the surgical procedures, but which could also be explained by concurrent disease or other drugs or chemicals.

Definitely Related: A clinical event, including laboratory test abnormality, with a reasonable time sequence to the investigational product exposure or surgical procedures, unlikely to be attributed to concurrent disease or other drugs or chemicals, and which follows a clinically reasonable response.

8.1.2. Expected Adverse Reactions

Refer to **Section 1.4.2.1**.

8.1.3. Determination of Abnormal Laboratory Test Values or Abnormal Clinical Findings as Adverse Event

The criteria for determining whether an abnormal, objective test finding should be reported as an AE are as follows:

- Test result is associated with accompanying symptoms, and/or
- Test result is not associated with a known, pre-existing condition or part of the subject's medical history, and/or
- Test result requires additional diagnostic testing or medical/surgical intervention, and/or
- Test result leads to discontinuation from the study, significant additional concomitant drug treatment, or other therapy, and/or
- Test result is considered to be an AE by the Investigator or sponsor.

Merely repeating an abnormal test, in the absence of any of the above conditions, does not constitute an AE. An abnormal test result determined to be an error does not require reporting as an AE.

Evidence of product sensitization (the presence of any donor anti-HLA antibodies absent prior to implant) is not, in itself, considered an AE. The above criteria should also be utilized to determine if the sensitization qualifies as an AE.

8.1.4. Adverse Events of Special Interest (AESI)

Certain AEs may require additional investigation to ensure appropriate information and data are captured to appropriately evaluate the clinical development of VC-01. These are considered adverse events of special interest (AESI) and may include but are not limited to:

- AEs leading to the unexpected or premature explantation of sentinel or dose-finding (VC-01-DF) units are considered AESI.
- AEs that result in early withdrawal from the study.
- Severe hypoglycemic events occurring after VC-01 implantation possibly or definitely related to VC-01.

If an AESI occurs, the Sponsor may request that additional data be collected for these events.

